Study Protocol and Statistical Analysis

[figure not shown]
A. Study Protocol

1. Research subjects

The research subjects were patients with CHB receiving ETV or second-line NA (LAM/ADV/LdT) who were admitted to The Second Affiliated Hospital of Chongqing Medical University and other centers.

2. Research design

96-week multi-centre prospective real world study

3. Research methods

In our hospital, about 150 patients are screened for HBV-DNA every day. Therefore, 54 million patients will be tested for HBV-DNA within one year, of which 30% are estimated to be HBV-DNA ≥ 10 IU. These patients will be informed to the Department of Infectious Diseases of the Second Affiliated Hospital of Chongqing Medical University for follow-up, and will be randomly divided into three groups according to 1:1. Patients in all three groups will be educated about hepatitis B virus infection and antiviral treatment, and the treatment regimen will be adjusted according to whether their HBV DNA is ≥ 10 IU/ml or not. Patients in group 1: patients with persistent low level HBV DNA (< 10 IU/ml). Patients in group 2: HBV-DNA ≥ 10 IU/ml, receiving HBV-related education and being advised by the doctor to change or to add another NA. Patients in group 2: patients with persistent HBV DNA (> 10 IU/ml) but refuse to change the regimen. Patients in group 3: patients with persistent HBV DNA (> 10 IU/ml) and agree to change the regimen. Educational methods include videos, including an introduction to hepatitis B virus (disease profile, infection, outcome, HBV infection, vertical transmission and other risk factors) for 5 minutes, brochures with relevant information and consultations with physicians and nurses.

All patients with CHB receiving ETV or second-line NA (LAM/ADV/LdT) treatment for more than six months to one year will receive HBV-DNA

detection, and patients with HBV-DNA \geq 10 IU/ml will be informed and recommended to adjust the treatment regimen so that we could obtain the actual prevalence of HBV-DNA load $<$ 10 IU/ml in Chongqing HBV cohort. We estimated that 30% of the patients had HBV-DNA \geq 10 IU/ml, so there were about 16,200 patients had HBV-DNA \geq 10 IU/ml among 54,000 patients a year. These patients will be diagnosed with LLV and will undergo a treatment regimen adjustment, with a recommendation to switch to or use a different type of NA for viral treatment.

4. Outcome indexes

(i) The main index:

The proportion of patients who received a complete virologic response (HBV DNA $<$ 10 IU/ml) at 24 weeks after therapy adjustment.

(ii) The secondary index:

1. The proportion of patients with complete virologic response (HBV DNA $<$ 10 IU/ml) at 12 weeks, 48 weeks and 96 weeks after therapy adjustment.

2. The proportion of patients with normal ALT at baseline and at each follow-up time point.

3. Changes of bone and kidney indicators (eGFR, SCr, BMD, etc.) compared with baseline at each follow-up time point.

B. Statistical Analysis

1. Statistical description

. Whether the measurement data conforms to normal distribution: the statistical method is modified or the data is converted when the measurement data does not conform to normal distribution, then it is managed as normal distribution when the mean and median are close due to the large sample size because of the opening test. Outliers: Statistical and professional analysis is performed to determine whether to keep outliers. Management of missing value in major efficacy indicators data: when a major efficacy data is missing in individual subjects, the method of filling is determined from a statistical and professional perspective. If the case is lost, data from the previous measurement shall be transferred.

. Case analysis of unfinished tests: the reason of lost cases should be analyzed one by one.

. Descriptive statistics: indicating the mean, the standard deviation, the maximum, the minimum, the median, the upper and lower quartile (Q1 and Q3), the confidence interval, the frequency (composition ratio), etc.

2. Statistical inference method

. The measurement data: T test, paired T test, rank sum test, paired

rank sum test, correlation analysis was used. The counting data: Chi-square test, Fisher exact test, etc. The grade data were tested by CMH method.

3. Statistical expression

- . The report is mainly expressed in tables, which are self-explanatory, that is, with headings, notes and main statistical indicators.
- . The results of repeated measurements are presented in tables with statistical charts for readability. F value and P value of an OVA of repeated measurement data are added.
- . Bilateral tests are generally used for statistical tests, and P less than or equal to 0.05 is considered to be statistically significant.

4. Statistical software

SPSS22.0 software will be used for analysis.

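### Allocation is described as 1:1 random, but HBV DNA level and the patient's own choice define the three groups, and no adjusted analysis is planned

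*Combined protocol and SAP*

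**What the plan says.** Section A.2 (Research design) describes a "96-week multi-centre prospective real world study" and does not mention randomisation. Section A.3 (Research methods) first identifies patients with HBV DNA at or above 10 IU, then says that they "will be randomly divided into three groups according to 1:1". The same paragraph defines the groups:

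- Group 1, by viral load below the threshold: "Patients in group 1: patients with persistent low level HBV DNA (< 10 IU/ml".
- Group 2, first definition, at or above the threshold: "receiving HBV-related education and being advised by the doctor to change or to add another NA".
- Group 2, second definition: "patients with persistent HBV DNA (> 10 IU/ml) but refuse to change the regimen".
- Group 3: "patients with persistent HBV DNA (> 10 IU/ml) and agree to change the regimen".

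The next paragraph of A.3 says of the patients at or above 10 IU/ml: "These patients will be diagnosed with LLV and will undergo a treatment regimen adjustment". That sentence goes on to mention a recommendation to switch to, or use, another type of NA.

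The main index in A.4 is the proportion with HBV DNA below 10 IU/ml "at 24 weeks after therapy adjustment". Sections B.2 and B.3 list t and paired t tests, rank sum and paired rank sum tests, correlation, chi-square, Fisher exact (followed by an open-ended etc.), CMH for grade data, and repeated-measures ANOVA. They name no covariate, stratum, regression model, matching or weighting, and no between-group contrast for the main index.

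**The concern.** A laboratory value and a patient's decision cannot be randomly assigned, so the allocation sentence and the group definitions cannot both be true. Randomisation is what would justify an unadjusted comparison, and without it the listed tests offer no protection.

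The natural contrast, although the plan never states it, is group 3 against group 2: both are above the threshold and they differ in whether the regimen changed. People who accept a change may differ from those who refuse in ways that also affect virological response. A crude difference then mixes the effect of changing with the reasons for agreeing or refusing. It could create a difference that is not there or conceal one that is. In a comparison of group 1 with the others, the outcome variable at baseline defines the group, so part of any difference is built in.

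A reader told that allocation was random would have no reason to look for any of this. Reporting the study as randomised would overstate the evidence.

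**Working it through.** **1. The plan's own count.** The only planning figure is the yearly pool above the threshold: 150 per day × 360 days = 54,000, and 54,000 × 0.30 = 16,200, as stated. It is a screening count, not an enrolment target, and this point does not depend on it.

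**2. Can the allocation sentence be true?** There are two readings of who is divided.

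- *Only patients at or above 10 IU.* This is the literal reading. Nobody can then enter group 1, which requires a value below 10 IU/ml.
- *All tested patients.* HBV DNA then decides group 1 against groups 2 and 3, and agreement or refusal decides group 2 against group 3. Nothing is left for chance to assign.

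Allocation is not random under either reading. A 1:1 ratio also does not describe three groups.

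**3. Are the groups well defined?** Group 2 has two definitions: advised to change or add a drug, and refuses to change. The first could also describe a patient who then agrees, that is, a group 3 patient. The statement that patients above the threshold undergo adjustment sits badly with a group that does not. The main index runs from adjustment, so week 24 has no starting point for refusers.

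**4. Is there any adjustment?** The main index is binary, so chi-square or Fisher applies, and both are unadjusted. CMH can be stratified, but it is listed for grade data with no strata named. An open etc. pre-specifies nothing.

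**5. How large could the bias be?** The documents give no response rates, prognostic factors or group sizes, so this is an illustration and every input is assumed. Take one binary factor, with week-24 response 45% if present and 20% if absent, and no true effect of changing.

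Crude rate = prevalence × 0.45 + (1 − prevalence) × 0.20.

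- Factor in 60% of group 3 and 40% of group 2: 0.6×0.45 + 0.4×0.20 = 0.35 against 0.4×0.45 + 0.6×0.20 = 0.30, a spurious +5 points. Reversed imbalance: −5 points.
- Factor in 55% and 45%: 0.3375 against 0.3125, a spurious 2.5 points.

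The rejection probability of the two-sided 5% pooled two-proportion test is Φ[(|d| − 1.96·SE₀)/SE₁] + Φ[(−|d| − 1.96·SE₀)/SE₁]. Here d is the crude difference, SE₀ the pooled and SE₁ the unpooled standard error. For 60%/40% at 500 per group, SE₀ = √(0.325×0.675×2/500) = 0.0296 and SE₁ = √((0.35×0.65 + 0.30×0.70)/500) = 0.0296, giving 0.393.

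| Group 3 n / group 2 n | 60% vs 40% | 55% vs 45% |
|---|---|---|
| 200 / 200 | 0.187 | 0.083 |
| 500 / 500 | 0.393 | 0.135 |
| 800 / 200 | 0.261 | 0.100 |
| 200 / 800 | 0.282 | 0.107 |

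With equal prevalence the rate is 0.050.

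**6. The other direction.** Suppose changing truly adds 5 points in each stratum (50% and 25% in group 3), with the factor in 40% of group 3 and 60% of group 2. Group 3: 0.4×0.50 + 0.6×0.25 = 0.35. Group 2: 0.6×0.45 + 0.4×0.20 = 0.35. The effect disappears.

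**7. Sensitivity to the assumptions.** With response 60% against 30% and the factor in 70% of one group and 30% of the other, the spurious difference is 12 points (51% vs 39%). With response 50% against 40% and prevalence 60%/40%, it is 2 points. Size and sign depend wholly on the inputs.

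**8. Does adjustment help?** In 4,000 simulated trials at 500 per group with no true effect, the crude test rejected in 39.8% (60%/40%) and 38.9% (40%/60%). Logistic regression including the factor rejected in 5.1% and 4.7%, with mean adjusted risk differences of 0.0002 and 0.0004. At 800/200 (60%/40%), crude was 26.9% and adjusted 5.0%.

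**The case against.** The strongest reply is that the confounding is conditional. No between-group contrast is stated. Read literally, the main index exists only for patients whose therapy was adjusted, so it could be a single-group estimate. The bone and kidney outcomes are changes from baseline, and paired tests are listed. This stands in part: group 3 against group 2 is an inference, though three groups and unpaired tests make a comparison likely. It does not rescue the allocation sentence, and leaving the contrast unnamed is itself a gap.

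Second, the text shows only that two statements conflict. A real-world study can be randomised, and the first definition of group 2 reads like an assigned intervention. But that definition is followed by a second based on refusal, and group 3 rests on agreement, so the sentence is wrong as the plan now stands.

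Third, the sentence saying that patients will undergo adjustment continues with a recommendation, which a patient may decline. That softens the conflict with a refusal group without removing it. It calls for reconciled wording, not a finding of its own.

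Fourth, the illustration is not evidence about this study, and the simulated adjustment works because it includes the only confounder built in. Both points are right. The figures show scale and mechanism only, and the model proposed is one option among several.

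**Conclusion.** The point holds and must be fixed. That the allocation statement is incompatible with the group definitions follows from the text alone and needs no assumption. That the plan names no adjusted analysis is equally plain. That a comparison would be confounded depends on groups 2 and 3 being compared and on agreement being related to prognosis. The documents give neither the size nor the direction. Under the assumed inputs of 45% and 20% response, with prevalence 55%/45% or 60%/40%, the bias is 2.5 to 5 points in either direction. The false-positive rate is then 8% to 39% at the group sizes tried, against a nominal 5%. Other assumptions give smaller or larger figures.

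**What to change.** 1. Replace the randomisation sentence in A.3 with a description of a non-randomised prospective cohort, with group 1 drawn from patients below 10 IU/ml.
2. Reconcile the two definitions of group 2, and reconcile the statement that patients undergo adjustment with the existence of a refusal group.
3. Name group 3 against group 2 as the primary between-group contrast. Give both groups a common time zero, for example the visit at which the change is recommended, and set the group by the decision recorded at that visit.
4. Pre-specify one adjusted model for week-24 response. One choice is logistic regression reporting an adjusted risk difference with 95% CI, with baseline log10 HBV DNA, ALT, eGFR, entry NA (ETV, LAM, ADV, LdT) and centre as covariates.
5. Keep chi-square as descriptive, and word the conclusion as an adjusted association.

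The cost is wording in both parts of the document and modest analysis work. HBV DNA, ALT and eGFR are already study outcomes, and entry NA and centre are known at enrolment. The claim becomes weaker than a randomised one, and residual confounding remains, including by factors such as adherence that the documents do not record.

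### The plan calls the three groups a random 1:1 division, but viral load and patient choice form them, and group 2 is defined in two incompatible ways

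*Combined protocol and SAP*

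**What the plan says.** Section A.2 describes a prospective real-world study. Section A.3 (Research methods) estimates the share of tested patients at or above the threshold ("of which 30% are estimated to be HBV-DNA ≥ 10 IU") and says that these patients "will be randomly divided into three groups according to 1:1".

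The groups are then defined as follows:

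- Group 1: "Patients in group 1: patients with persistent low level HBV DNA (< 10 IU/ml").
- Group 2, first sentence: "Patients in group 2: HBV-DNA ≥ 10 IU/ml, receiving HBV-related education and being advised by the doctor" to switch or add a drug.
- Group 2, next sentence: "Patients in group 2: patients with persistent HBV DNA (> 10 IU/ml) but refuse to change the regimen".
- Group 3: "patients with persistent HBV DNA (> 10 IU/ml) and agree to change the regimen".

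The same section says "Patients in all three groups will be educated about hepatitis B virus infection and antiviral treatment", and that "the treatment regimen will be adjusted according to whether their HBV DNA is ≥ 10 IU/ml or not". Its second paragraph has every patient at or above 10 IU/ml told of the result and recommended a change. It puts the yearly numbers at 54,000 tested and about 16,200 at or above 10 IU/ml, and says that those patients undergo an adjustment.

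Section A.4 sets the main index as the proportion below 10 IU/ml at 24 weeks after therapy adjustment. For counts, section B.2 lists the chi-square and Fisher exact tests, among others not named. It specifies no between-group contrast.

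**The concern.** Random allocation means that chance decides the group. Here a laboratory value decides group 1, and the patient's own decision separates group 2 from group 3. Patients who accept a change may differ from those who decline in ways that also affect virologic response. If the text calls the division random, a reader of the results could take a group 3 versus group 2 difference as a causal effect of changing treatment, which this design does not support.

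The double definition adds a second problem. Group 2 membership determines any between-group result on the main index, and two consecutive sentences give it different members.

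**Working it through.** **Input to settle first.** The opening of A.3 gives the yearly total as 54 million; the later paragraph gives 54,000. At 150 patients a day, 150 × 360 = 54,000 (150 × 365 = 54,750), so 54,000 is the figure that fits. Then 0.30 × 54,000 = 16,200, which reproduces the plan's number, and 54,000 − 16,200 = 37,800 lie below 10 IU/ml. These are screening counts, not enrolment; the documents state no enrolment number.

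**Can a random equal division produce these groups?** The text leaves open which patients are divided.

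- If only those at or above 10 IU/ml are divided: 16,200 / 3 = 5,400 per group, but group 1 requires a value below 10, so it has 0 candidates.
- If everyone tested is divided: 54,000 / 3 = 18,000 per group, so groups 2 and 3 together need 36,000. At most 16,200 are eligible. Group 1 could draw on up to 37,800.

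The second result does not depend on the total: equal thirds need two thirds of patients at or above the threshold, and the plan estimates 30%. Nor can education be what is randomised, because all three groups receive it.

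**Who belongs to group 2?** The table takes values as persistent and patients at or above 10 as educated and advised.

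| HBV DNA (IU/ml) | Decision | Group 1 | Group 2, first sentence | Group 2, second sentence | Group 3 |
|---|---|---|---|---|---|
| < 10 | either | yes | no | no | no |
| = 10 | either | no | yes | no | no |
| > 10 | agrees | no | yes | no | yes |
| > 10 | refuses | no | yes | yes | no |

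The first sentence sets no condition on the patient's decision, so it contains all of group 3. The second shares no patient with group 3. A value of exactly 10 fits only the first sentence; under the second it falls in no group.

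**Effect of using the first sentence literally.** Let *a* be the share who accept, *p3* the response rate in accepters and *p2* the rate in refusers, with all patients persistent. None of these is in the documents.

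- Group 2 rate = *a·p3* + (1 − *a*)·*p2*
- Group 3 minus group 2 = *p3* − [*a·p3* + (1 − *a*)·*p2*] = (1 − *a*)(*p3* − *p2*)

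For an assumed 20-point difference:

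- *a* = 0.3: 0.7 × 20 = 14 points
- *a* = 0.5: 0.5 × 20 = 10 points
- *a* = 0.7: 0.3 × 20 = 6 points

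**The case against.** The best defence is that the first group 2 sentence is a drafting slip. Dividing patients into three groups implies a partition, and the refuse and agree sentences form a matched pair. That is probably right, and nothing in the plan says that an accepter will be counted twice. It follows that the dilution above is conditional, not predicted. The slip does not explain the randomisation statement or the switch from ≥ 10 to > 10.

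It could also be said that equal group sizes might be reached by recruiting a fixed number into each group. That would give equal numbers, but not a random division.

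Three stronger readings are tempting, and the documents do not support them:

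- *The overlap costs the study its power.* This needs the first sentence to be used literally, plus assumed acceptance and response rates and an assumed sample size. At the only documented scale, 16,200, power stays at about 100% even for an assumed 10-point difference with 70% acceptance (rates symmetric around 50%, z about 4.9).
- *The main index has no week 0.* It can be read as a proportion among patients whose therapy was adjusted, and for them the starting point is defined. The gap arises only if the index is also applied to refusers.
- *The plan leaves no room for refusal.* Some sentences do say that the regimen will be adjusted, but the section also speaks of a recommendation, which a patient can decline. The sentences need reconciling; they do not rule out a refusing group.

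**Conclusion.** The concern holds. The statement of random 1:1 division is wrong as written: the group definitions leave nothing to randomise, and on the plan's figures equal random thirds cannot be formed under either reading of who is divided. This needs no outside assumption beyond taking 54,000, not 54 million, as the intended total; on the all-patients reading, the 30% estimate alone is enough.

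Group 2 has two incompatible definitions, the first of them probably a mislabel. If it were used literally, a group 3 versus group 2 difference would be multiplied by (1 − acceptance share), with all patients taken as persistent. The documents give no acceptance share, and that contrast is itself inferred from the group structure. The matter should be corrected before analysis, chiefly because the random label invites a causal reading of self-selected groups.

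**What to change.** 1. Remove the statement of random 1:1 division. Describe the groups as non-randomised, formed by viral load and patient decision.
2. State which sentence defines group 2. The reading that fits a three-way division is to relabel the first sentence as a description of what all patients at or above 10 IU/ml receive, and to define mutually exclusive analysis groups: declines the change (group 2) and accepts it (group 3).
3. Use one analysis cut-off for groups 2 and 3 that is complementary to the < 10 IU/ml endpoint, so that a value of exactly 10 has a place.
4. Report any group 3 versus group 2 comparison as observational, not as a randomised effect.
5. If the main index is compared with refusers, use one common week 0 for groups 2 and 3, for example the date of the advice, because group 2 has no therapy adjustment to count from.
6. Reconcile the sentences saying that the regimen will be adjusted with the existence of a group that declines. This concerns the wording and the analysis groups only; no treatment rule is proposed.
7. Correct the 54 million figure so that it agrees with the later 54,000.

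The cost is mainly rewording, plus one extra recorded date if refusers are compared. The causal claim becomes weaker, and self-selection remains: disjoint groups do not remove it, and section B.2 names no adjusted method for comparing response proportions between accepters and refusers.

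### Entry to groups 2 and 3 is defined in conflicting ways around the same 10 IU/ml cut-off as the main index, so falls unrelated to treatment may count as response

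*Combined protocol and SAP*

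**What the plan says.** Section A.3 (Research methods) states the entry condition in several ways.

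- **Group 2, one version:** HBV DNA ≥ 10 IU/ml, "receiving HBV-related education and being advised by the doctor to change or to add another NA". Persistence is not mentioned.
- **Group 2, other version:** "patients with persistent HBV DNA (> 10 IU/ml) but refuse to change the regimen".
- **Group 3:** "patients with persistent HBV DNA (> 10 IU/ml) and agree to change the regimen".
- **Screening paragraph:** patients at or above "10 IU/ml will be informed and recommended to adjust the treatment regimen".
- **Consequence of screening:** "These patients will be diagnosed with LLV and will undergo a treatment regimen adjustment". Persistence is again not mentioned, and the sentence leaves no room for the patients who refuse.

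No number of tests, interval or assay is given for persistence, and no confirmatory test is described. Section A.4 defines the main index as the proportion below 10 IU/ml "at 24 weeks after therapy adjustment". It names no comparison between groups.

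**The concern.** Two features combine.

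1. **The entry rule is unsettled.** Two centres could both follow A.3 while one admits a patient on a single value of 10 or more and the other waits for repeated values above 10. A value of exactly 10 triggers advice but fits neither of the definitions written with a strict inequality.
2. **Entry and response share one cut-off.** Patients selected because a measurement exceeded 10 IU/ml will in part read below 10 when measured again, with no change of treatment. The main index is written for patients after adjustment and without a comparator, so it would count those falls as response.

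At stake is whether the headline proportion can be attributed to changing the regimen. A second question is whether groups 2 and 3 are comparable at entry, apart from the patient's choice.

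**Working it through.** **Step 1. The plan's own figure.** A.3 says "about 150 patients are screened for HBV-DNA every day". 150 × 360 days = 54,000 a year, and 0.30 × 54,000 = 16,200, as stated. This counts results at or above 10 in screening, with no persistence condition. It is a screening yield and is not in dispute here.

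**Step 2. The rules side by side.**

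| Place in A.3 | Inequality | Persistence |
|---|---|---|
| Referral, advice, diagnosis, 16,200 | ≥ 10 | not mentioned |
| Group 2, advised | ≥ 10 | not mentioned |
| Group 2, refuses | > 10 | required, undefined |
| Group 3, agrees | > 10 | required, undefined |

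**Step 3. How many patients would fall below 10 with no change?** The only input from the documents is the 30% at or above 10 IU/ml (1 log10). Assumed inputs are a between-patient SD (σB) of 0.6 to 1.0 log10, a within-patient SD (σW) of 0.2 to 0.4 log10, normality on the log scale, and no trend over time. The correlation between repeat values is ρ = σB² / (σB² + σW²).

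Let p be a patient's own probability of a result ≥ 10, and m_k the mean of p^k over patients, with m_1 = 0.30. Then:

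- P(later < 10 | one result ≥ 10) = 1 − m_2/m_1
- P(later < 10 | two results ≥ 10) = 1 − m_3/m_2

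| σB, σW | ρ | m_2 | m_3 | After one result | After two results |
|---|---|---|---|---|---|
| 1.0, 0.2 | 1/1.04 = 0.96 | 0.261 | 0.243 | 13% | 7% |
| 0.8, 0.4 | 0.64/0.80 = 0.80 | 0.211 | 0.172 | 29.6% | 18.5% |
| 0.6, 0.4 | 0.36/0.52 = 0.69 | 0.189 | 0.142 | 37% | 25% |

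Over a wider assumed range of ρ, 0.95 down to 0.5, the shares run from 14.7% to 47.7% after one result and from 8.1% to 35.7% after two. Requiring two results reduces the effect but does not remove it.

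**Step 4. What happens to the contrast between groups 3 and 2?** Take ρ = 0.80 and assume, for illustration, that changing suppresses half of those who would otherwise stay at or above 10. Group 3 response is then s + 0.5(1 − s), where s is the share falling with no change. That is 64.8% after one-result entry (s = 29.6%) and 59.2% after two-result entry (s = 18.5%). Differences below come from unrounded values.

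| Entry rule | Group 3 | Group 2 | Difference (points) |
|---|---|---|---|
| Both on one result | 64.8% | 29.6% | 35 |
| Both on two results | 59.2% | 18.5% | 41 |
| Group 3 on one, group 2 on two | 64.8% | 18.5% | 46 |
| Group 2 on one, group 3 on two | 59.2% | 29.6% | 30 |

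If changing had no effect, the third row would still show 29.6% − 18.5%, about 11 points in favour of changing. The fourth row would show about 11 points against it. Under a shared rule, both groups carry the same share of spontaneous falls, and single-result entry gives a smaller difference than two-result entry.

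**The case against.** The strongest reply is that A.3 can be read in two stages: patients at or above 10 are referred for follow-up, then grouped once viraemia proves persistent. All three groups carry the word persistent in at least one definition, including group 1 (below 10). The documents nowhere say that one result suffices; they are silent on the number of tests. This stands, so mixed entry is possible but not shown. It does not remove the defect, because the second paragraph of A.3 moves from a value ≥ 10 to diagnosis and adjustment without mentioning persistence.

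A reader might also infer three stronger things that the documents do not support.

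- **That the comparison is biased in favour of changing.** This needs group 3 to have the looser rule. The duplicate definition of group 2 points, if anything, to the opposite mix, which shrinks the contrast.
- **That single-result entry inflates the difference between groups.** Under a shared rule it does not (35 against 41 points in the illustration).
- **That the 30% prevalence or the 16,200 is wrong.** A.3 seeks the share below 10 IU/ml at testing, a cross-sectional quantity that persistence does not enter.

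Finally, the size is wholly assumed, since no within- or between-patient SD is given. That also stands, so the figures show a range and are not an estimate for this cohort.

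**Conclusion.** The concern holds as an internal contradiction with a conditional bias. The contradiction can be seen directly in A.3: two inequalities, two definitions of group 2, and persistence required in some places, absent in others and never defined.

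The bias follows if one result suffices for entry. The uncontrolled group 3 proportion would then include patients who would have read below 10 anyway: 13% to 37% under the assumed SDs, against 7% to 25% with two results. The group 3 minus group 2 contrast is distorted only if the two groups enter under different rules, and the sign depends on which rule is looser.

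The point deserves action before analysis because it bears on the main index. Confidence in the size is low because it rests on assumed repeatability. Forming the groups by patient choice, although A.3 speaks of random division, is a separate and larger threat to the comparison.

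**What to change.** 1. **One entry definition.** The sponsor must reconcile the passages of A.3: state what persistent means (number of tests, interval, assay), use one inequality, and keep one definition of group 2. The rule should apply identically to groups 2 and 3 before the patient decides. The clinical trigger for advice is the sponsor's to set.
2. **A named comparison.** State the main analysis as the group 3 minus group 2 difference in the proportion below 10 IU/ml at 24 weeks. Count from a common time zero, for example the date of advice, because group 2 refuses adjustment and so has no start date under A.4.
3. **Adjustment.** Adjust for baseline HBV DNA. For count data, section B.2 names only the chi-square and Fisher tests, so an adjusted method must be added, such as logistic regression with a standardised risk difference. Describe the comparison as non-randomised.
4. **Sensitivity analysis.** Where an earlier on-treatment result exists, repeat the analysis in patients whose earlier result was also at or above the cut-off. The documents do not say how many have one.

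The cost is protocol and SAP wording plus one extra analysis of existing data. The downsides are a smaller sensitivity set and a less favourable headline than the uncontrolled proportion. A stricter entry rule alone is not enough, since two results still leave 7% to 25% under the same assumptions; the concurrent comparison is what deals with the remainder.

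### LLV has no upper viral-load limit and the main index is pooled and unadjusted, so the week 24 result reflects baseline case mix and cannot be attributed to LLV

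*Combined protocol and SAP*

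**What the plan says.** **Who is tested.** A.3 Research methods: "All patients with CHB receiving ETV or second-line NA (LAM/ADV/LdT) treatment for more than six months to one year will receive HBV-DNA" detection.

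**Who is called LLV.** A.3 puts the share at or above 10 IU/ml at 30%, about 16,200 of 54,000 a year, and continues: "These patients will be diagnosed with LLV and will undergo a treatment regimen adjustment". LLV is not defined anywhere else, and no upper HBV DNA limit appears in A.1, in the group definitions or in this sentence.

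**The groups.** The two viraemic groups have a floor only. In its second definition, group 2 is "patients with persistent HBV DNA (> 10 IU/ml) but refuse to change the regimen". Group 3 is "patients with persistent HBV DNA (> 10 IU/ml) and agree to change the regimen". No number of tests, interval or duration is attached to the word persistent.

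**The endpoint.** The main index in A.4 is "The proportion of patients who received a complete virologic response", meaning HBV DNA below 10 IU/ml, 24 weeks after adjustment. The first secondary index repeats it at weeks 12, 48 and 96.

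**The analysis.** B.2 names chi-square and Fisher tests for counted data and reserves CMH for graded data. Section B names no subgroup, stratification or adjustment by baseline HBV DNA or by time on treatment.

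**The concern.** A patient at 50 IU/ml and one at 10,000 IU/ml carry the same label and enter the same proportion, although reaching the same threshold asks very different things of them. Patients only just past six months of treatment may still be falling on their current regimen, and some could pass below 10 IU/ml by week 24 without any change.

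Two things are at stake. First, a single pooled percentage would depend on who happened to be enrolled, so it could not be reported as the response of LLV or carried to a clinic with a different mix. Second, membership of groups 2 and 3 turns on the patient's own refusal or agreement. If that decision is related to viral load, an unadjusted comparison would attribute a difference in starting level to the regimen.

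**Working it through.** **1. The plan's own count.** Inputs from A.3: 150 tests a day and a 30% share. 150 × 360 = 54,000 (150 × 365 = 54,750). 0.30 × 54,000 = 16,200. The count reproduces. The LLV count equals the whole count at or above 10 IU/ml, so nobody is removed for a high viral load.

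**2. Fall needed to respond.** Required fall = log10(baseline) − log10(10). This needs no assumption about treatment.
- From 50 IU/ml: 1.7 − 1.0 = 0.7 log10.
- From 10,000 IU/ml: 4.0 − 1.0 = 3.0 log10.

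**3. Effect on the pooled main index.** The plan gives no response rates, so these are assumptions. Take a 24-week fall that is normal with mean 2.0 and SD 0.8 log10 in every patient.
- From 50 IU/ml: Φ((2.0 − 0.7)/0.8) = 0.948.
- From 10,000 IU/ml: Φ((2.0 − 3.0)/0.8) = 0.106.
- 10% at the high level: 0.9 × 0.948 + 0.1 × 0.106 = 0.864.
- 40% at the high level: 0.6 × 0.948 + 0.4 × 0.106 = 0.611.

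The index moves by 25.3 points with an identical treatment effect. In general the shift is (0.40 − 0.10) × the difference in response between the two levels. With milder assumed rates of 50% and 15%, it is 0.30 × 35 = 10.5 points.

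**4. Effect on group 2 versus group 3.** Assume no treatment effect, with response of 50% in LLV and 15% in higher viraemia whichever group the patient is in. Group response = (1 − h) × 0.50 + h × 0.15, where h is the share with higher viraemia.

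| h, group 2 (refuse) | h, group 3 (agree) | Group 2 | Group 3 | Spurious difference (3 − 2) |
|---|---|---|---|---|
| 20% | 20% | 43.0% | 43.0% | 0 |
| 10% | 30% | 46.5% | 39.5% | −7.0 points |
| 10% | 40% | 46.5% | 36.0% | −10.5 points |
| 30% | 10% | 39.5% | 46.5% | +7.0 points |

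**5. Dilution with equal mix.** Assume LLV response of 30% without and 60% with a change, a difference of 30 points. The pooled difference is (1 − h) × 30 + h × d, where d is the difference in the other patients. For h = 10%, 30% and 50%:
- d = 0: 27, 21 and 15 points.
- d = 10: 28, 24 and 20 points.

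**6. Early-treatment patients.** Assume 30 IU/ml at baseline and a continuing fall on an unchanged regimen over about 5.5 months. At 0.1 log10 a month, 30 × 10^(−0.55) = 8.5 IU/ml, a response. At 0.05 log10 a month, 30 × 10^(−0.275) = 15.9 IU/ml, a non-response.

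**The case against.** The plan describes a real-world study, and broad inclusion is legitimate in one. LLV appears once and no hypothesis about it is stated. A reader might infer that the main index cannot answer the study's question at all. The documents do not support that: it answers a question about any viraemia at or above 10 IU/ml on treatment. What fails is attribution to LLV.

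The viraemic groups are described as persistent, which is some protection against transient or still-falling values. But the word is undefined, sets no ceiling, and does not appear in the sentence that applies the LLV label.

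Group 2 stays on its regimen, so a continuing fall on unchanged treatment would show there too. This does blunt step 6. The protection is partial: the group is self-selected, the main index names no comparison, and it is timed from an adjustment that group 2 does not have. A.3 also mentions random division, but that cannot balance groups defined by refusal and agreement.

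The list of tests for counted data in B.2 is open-ended, so an adjusted analysis is not ruled out. Neither is it specified.

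The sizes above are illustrations. The mean fall and SD in step 3 are single assumed values, and the 30 IU/ml start in step 6 makes the two rates fall either side of the threshold. This stands: the true viral-load distribution is not in the documents.

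Two further inferences should be resisted. Group 1, below 10 IU/ml, is also described as low level ("Patients in group 1: patients with persistent low level HBV DNA"). That is a wording fault and not evidence of mixing. Nor do the documents support resting the LLV conclusion on patients with at least one year of treatment. If "treatment for more than six months to one year will receive HBV-DNA" describes a window with a one-year ceiling, that set would be nearly empty. If it describes a range of minimum durations, it would not.

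**Conclusion.** The concern holds as a matter of definition and analysis. LLV has a floor and no ceiling, persistence is undefined, the duration phrase is ambiguous, and a fixed-threshold endpoint is to be pooled and tested without regard to baseline HBV DNA. That the required fall differs (0.7 against 3.0 log10 in the example) is arithmetic. That the index will therefore depend on case mix follows if patients at higher levels respond less often.

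The size cannot be computed from the plan. Under the stated assumptions, the pooled index moves by 10.5 to 25.3 points when the high-viraemia share goes from 10% to 40%. A null comparison of groups 2 and 3 can show 7 to 10.5 points in a direction set by the imbalance, and nothing if the mix is equal. The result would be valid as a description of everyone at or above 10 IU/ml in these centres, but not as the response of LLV to a regimen change.

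**What to change.** **Section B (the main change).** Report the week 24 main index and the week 12, 48 and 96 virologic indexes by prespecified baseline HBV DNA bands. Compare groups 2 and 3 with adjustment for baseline log10 HBV DNA, for example by logistic regression, or with a CMH test stratified by baseline band. Add time on the current regimen where it is recorded.

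**Section A.3.** State the HBV DNA range and the persistence rule (number and spacing of tests) that define the LLV analysis set. Clarify the duration phrase first, then set any duration bands. Attribute conclusions to LLV only for that set, and otherwise to any viraemia at or above 10 IU/ml on treatment. These are definitions for analysis: they exclude no one from the study and change nobody's management.

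**Cost.** Mostly wording, since baseline HBV DNA is already measured at screening. Time on the current regimen has to be recorded as a value, not only checked against a minimum. Numbers per band will be smaller. The loss should not be judged against 16,200, because that figure is 30% of everyone screened, and the number of treated patients who enrol and change regimen is not given. Adjustment removes only the imbalance in what is measured, so groups 2 and 3 remain a self-selected comparison.
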